11.2. Endpoint Definitions

11.2.1. Part A Primary Endpoint

The primary endpoint for Part A is sensitivity of miRNA for relapse detection, defined as the number of relapses detectable on miRNA testing before or at the same time as detection on imaging (or via other components of standard surveillance) as a proportion of the total number of relapses identified via standard investigations. In all cases, date of detection will be taken to be the date of the sample collection or imaging/investigation (rather than the date the results were available) and a 2-week window will be allowed from detection on imaging/standard investigations to allow for scheduling of miRNA testing sometimes occurring after imaging. Detection on miRNA requires a positive result according to lab-specific normal ranges, and the date of sample collection will be taken to be the date of relapse detection.

11.2.2. Part A Secondary Endpoints

The following secondary endpoints will be evaluated during part A:

- Lead time for relapse detection on miRNA, defined as time between relapse detection on miRNA (date sample taken) and relapse detection on imaging (date of scan).

- Specificity of miRNA for relapse detection, defined as number of non-relapsing participants (based on imaging) whose miRNA levels remained negative (or indeterminate) throughout the follow-up period, as a proportion of all non-relapsing participants.
- Time from blood draw for miRNA testing to miRNA results being available to the clinical team (and participant), and the number (proportion) of results available within 2 weeks.
- Adherence to miRNA testing, defined as the number of samples taken for miRNA testing as a proportion of all scheduled tests; numbers of tests performed more than a 4-week window either side of the schedule time point and number of samples that could not be analysed will also be reported.
- Adherence to imaging schedules defined as the number of attendances for imaging as a proportion of all scheduled imaging; the number of scans performed; numbers of scans performed more than a 4-week window either side of the schedule time point will also be reported.
- Patient-reported acceptability of miRNA monitoring without routine surveillance imaging (using a trial-specific questionnaire based on a validated, generic instrument for evaluating acceptability of healthcare interventions^{35,36}).

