2.2. Secondary Objectives**Part A:**

- To demonstrate high specificity of miRNA for relapse detection in this setting
- To demonstrate feasibility and acceptability to patients of miRNA monitoring in this setting
- To quantify the lead time (extent to which relapse diagnosis can be bought forward) associated with miRNA monitoring when compared with standard surveillance

Part B:

- To demonstrate cost-effectiveness of miRNA monitoring compared with standard surveillance
- To demonstrate reduced use of imaging and subsequent impact on radiation exposure with miRNA monitoring compared with standard imaging-based surveillance
- To further evaluate acceptability to patients of miRNA monitoring in this setting
- To quantify anxiety, fear of recurrence and health-related quality of life for patients managed with the two different approaches to surveillance
- To understand any impact on disease outcomes and subsequent treatment associated with use of miRNA monitoring in place of standard imaging
- To understand the risk-benefit balance of a miRNA monitoring approach (when compared to standard surveillance) from the perspective of different stakeholders, including patients

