7.2. Surveillance Assessments

7.2.1. PART A

The following assessments should be conducted at the time points indicated. For scheduling purposes, a 2-week window either side of the actual time point is acceptable. Imaging should be performed within 2 weeks either side of the blood sample being taken for miRNA analysis.

3 months (m), 6m, 9m, 12m, 15m, 18m, 21m, 24m, 30m, 36m, 42m, 48m, 54m and 60m after registration in the trial.

- Routine tumour markers (AFP, β -HCG and LDH)
- Review/Reporting of SAEs as appropriate (see section 10)
- Collection of blood sample for miRNA analysis (except at 54m)* - described further in section 10
- **Required radiological assessments** (Ideally the same imaging modality should be used for surveillance throughout the trial.):
 - **For seminoma participants:** Cross-sectional abdominal imaging at 6m, 18m and 36m, preferably with MRI but CT can be used according to local practice.
 - **For dysgerminoma participants:** Cross-sectional abdominal+/-pelvic imaging at 6m, 18m and 36m, preferably with MRI. For participants under the age of 19, pelvic ultrasound (US) may be used at physician's discretion where MRI is not possible or where US is used routinely at site.
- **Additional imaging and assessments according to local practice:** In addition to the required radiological assessments above, the following can also be performed according to local practice:
 - cross-sectional imaging (abdominal+/-pelvic MRI or CT) can be performed at up to 4 further time points over the 5-year follow-up period
 - Physical examination
 - For seminoma, chest x-ray can be performed as per local practice
 - For dysgerminoma participants, low dose chest CT and transvaginal US can be performed as per local practice.
- Acceptability questionnaire to be completed by participant at 12m** (for participants 16 years old and over only)

*Note: miRNA samples taken at 9m, 15m, 21m and 42m will be analysed retrospectively in case of relapse only, and results will not be fed back to centres in real time.

**Note: Acceptability questionnaire (16 and over only) emailed or posted to participant's home address directly from ICR-CTSU, based on participant's preference, but site teams are asked to remind the participant about completion in order to maximise return rates.

7.3. Procedure for follow-up of positive routine tumour marker or finding on physical exam

[figure not shown]

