7.4. Procedure for follow-up of different miRNA results

Please refer to the flowchart below describing follow-up procedures according to miRNA results. In the event of a negative result, surveillance should continue as described in section 7.2.

1. AFP, β -HCG and LDH

* For dysgerminoma patients under the age of 19 US may be used at physician's discretion.

1. This would be the routine surveillance MRI/CT if the positive miRNA result occurred at a time point when routine imaging was planned (6, 18 or 36m).

2. US results managed as per local practice.

3. 1. AFP, β -HCG and LDH

4. miRNA sample to be analysed retrospectively.

5. Confirmed on repeat within 4 weeks.

6. In cases where the miRNA remains positive and no other scans are planned within the routine surveillance schedule, MRI/CT should be repeated 6 months after the 3m follow-up scan. If the miRNA remain positive with negative imaging, please contact the trial team to discuss.

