7.4.2. Procedure on receipt of a positive miRNA result or routine tumour marker

If the miRNA test returns a positive result or routine markers are positive (and remain positive on repeat testing as per section 7.3), the potential relapse should be confirmed by MRI or CT (as per local practice, ideally the same imaging modality should be used throughout the trial) of the abdomen and pelvis and CT of the chest. For dysgerminoma participants under the age of 19 US may be used at physician's discretion. A repeat miRNA test should also be performed.

- If imaging is positive, procedures at disease recurrence, as described in section 7.6, should be followed.
- If the imaging is negative, further investigation should be conducted with ^{18}F Fluoro-deoxy glucose (FDG) PET-CT. Ultrasound of contralateral scrotal testis should also be considered in seminoma participants.
- If the FDG PET-CT is negative, participants should be assessed 6 weeks after that scan with the following assessment:
 - Routine tumour markers (AFP, β -HCG and LDH)
 - Collection of blood sample for miRNA analysis (to be analysed retrospectively)
 - For seminoma patients, ultrasound of contralateral scrotal testis if not performed at time of PET-CT.
- If the routine tumour markers are elevated, this should be confirmed as described in section 7.3, and then imaging should be repeated (MRI or CT of the abdomen and pelvis and CT of the chest, Ideally the same imaging modality should be used for surveillance throughout the trial).
- If the routine tumour markers are not elevated, participants should be assessed again after a further 6 weeks (i.e. 12 weeks after PET-CT) with the following assessments:
 - Physical examination
 - Routine tumour markers (AFP, β -HCG and LDH)
 - Collection of blood sample for miRNA analysis
 - Imaging (chest CT and with either MRI or CT abdomen and pelvis as per local practice, consider including sanctuary sites such as brain). For dysgerminoma participants under the age of 19, US may be used at physician's discretion.

In the event that the miRNA result returns to normal during repeat testing as part of the above process, please contact the trial team to discuss ongoing management on a case-by-case basis.

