9.1.1. PART A Sample scheduling

Blood samples for miRNA testing will be collected at all protocol-mandated visits, with the exception of the 54-month visit, timed from registration as follows: registration, 3 months (m), 6m, 9m, 12m, 15m, 18m, 21m, 24m, 30m, 36m, 42m, 48m, 60m.

Samples collected at registration, 3m, 6m, 12m, 18m, 24m, 30m, 36m, 48m and 60m will be analysed in real time and results fed back to the centre. Samples collected at the other time points will be analysed retrospectively at the end of Part A for participants who relapsed during the trial. Results from these samples will not be fed back but will be used to provide more detailed information of the potential lead time for relapse detection on miRNA when compared with imaging.

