11.3.3. Part A Analysis Plan

Part A analyses will be largely descriptive. Sensitivity of miRNA will be presented with a 60% exact binomial confidence interval (CI), reflecting the design; 95% CIs will also be presented.

Time from blood draw to miRNA results being available will be summarised (median, interquartile range, range), both overall and by centre, and the proportion of results available within 2 weeks will be presented with a 95% CI. Adherence to miRNA testing and surveillance imaging will be presented as number (proportion) for each time point and also summarised at the patient level (i.e. number missing at least one test or scan). MiRNA results at each time

point will be summarised (negative, positive, or indeterminate) as well as the numbers of samples that could not be analysed.

Acceptability questionnaires will be scored and analysed using the methods described by Sekhon et al³⁵. Items assessing burden and opportunity costs will be reverse scored so that a higher score always indicates higher acceptability. For each patient, a single acceptability score will be computed as the total mean score for the seven items from the theoretical framework of acceptability; the general acceptability item and any trial-specific items will be reported separately. This will be a descriptive non-comparative analysis, reporting mean and standard deviation (or median and IQR if appropriate) for the composite acceptability score and, for individual items, the number and proportion of patients responding in each category. Responses to the general acceptability item will be correlated with individual items from the framework.

For the final analysis, specificity will additionally be presented with a 95% exact binomial confidence interval. Lead time (from detection on miRNA to detection on imaging) will be calculated considering miRNA results from additional samples, analysed retrospectively in relapsing patients. Central review of imaging for relapsing patients will be used to confirm the time that relapse detection was possible and will inform supplementary analyses considering the impact on estimates of sensitivity and specificity.

The Part A analysis will also incorporate comparison of patient and tumour characteristics of the seminoma cohort with the TRISST trial cohort to confirm the extent of heterogeneity and inform planned analyses in Part B.

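### For relapses confirmed on a scan that a between-scan miRNA positive triggered, Part A lead time ends at that brought-forward scan and so understates how far diagnosis is advanced against standard surveillance

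*Protocol*

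**What the plan says.** The secondary objective in Protocol section 2.2 is "To quantify the lead time (extent to which relapse diagnosis can be bought forward) associated with miRNA monitoring when compared with standard surveillance". Section 11.2.2 turns this into an endpoint, the "time between relapse detection on miRNA (date sample taken) and relapse detection on imaging (date of scan", and section 11.3.3 adds that "Lead time (from detection on miRNA to detection on imaging) will be calculated considering miRNA results from additional samples", meaning the stored samples tested later in relapsing patients. Neither section says whether the scan that closes the interval must be a routine one.

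Four other provisions decide which scan that is:

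- Section 9.1.1: "Samples collected at registration, 3m, 6m, 12m, 18m, 24m, 30m, 36m, 48m and 60m will be analysed in real time".
- Section 7.2.1: "miRNA samples taken at 9m, 15m, 21m and 42m will be analysed retrospectively in case of relapse only". These results do not go back to centres, so they cannot prompt a scan.
- Section 7.4.2: "If the miRNA test returns a positive result or routine markers are positive" (and, for markers, stay so on repeat), "the potential relapse should be confirmed by MRI or CT".
- Section 7.2.1 requires surveillance imaging at 6, 18 and 36 months and allows up to four further cross-sectional scans under local practice. A note to the flowchart in section 7.4 says of the scan after a positive result: "This would be the routine surveillance MRI/CT if the positive miRNA result occurred at a time point when routine imaging was planned".

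**The concern.** Lead time against standard surveillance needs two dates: when miRNA first showed the relapse, and when standard surveillance would have shown it. In Part A the second date is not left alone. A real-time positive between required scans leads to imaging soon afterwards, and if the relapse is visible that scan becomes the recorded imaging detection. The date on which standard surveillance would have found it is then never observed.

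For those relapses the recorded interval is mainly the wait for the triggered scan, plus any time gained from an earlier stored sample. The error runs one way, towards too short a lead time. It is largest where the next required scan is far off, which is where miRNA monitoring could bring diagnosis forward most.

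**Working it through.** The protocol gives no numerical lead time, so there is no figure to reproduce. The check compares two intervals from the first positive sample: to the confirming scan (as defined) and to the next required scan.

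**Inputs from the protocol.** Real-time samples at 3, 6, 12, 18, 24, 30, 36, 48 and 60 months (plus registration); stored samples at 9, 15, 21 and 42 months; required scans at 6, 18 and 36 months.

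**Assumptions for the hand calculation (not in the protocol).** miRNA onset uniform over 0 to 36 months; relapse visible on imaging as soon as miRNA is positive; tests perfect; triggered scan 1 month after the real-time sample; no local scans or marker detections.

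| First positive sample | Months of onset it covers | Confirming scan | Lead time as defined | Interval to next required scan |
|---|---|---|---|---|
| 3m | 3 | triggered, 4m | 1 | 3 |
| 6m | 3 | routine, 6m | 0 | 0 |
| 9m (stored) | 3 | triggered by 12m sample, 13m | 4 | 9 |
| 12m | 3 | triggered, 13m | 1 | 6 |
| 15m (stored) | 3 | routine, 18m | 3 | 3 |
| 18m | 3 | routine, 18m | 0 | 0 |
| 21m (stored) | 3 | triggered by 24m sample, 25m | 4 | 15 |
| 24m | 3 | triggered, 25m | 1 | 12 |
| 30m | 6 | triggered, 31m | 1 | 6 |
| 36m | 6 | routine, 36m | 0 | 0 |

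Mean = sum of (months covered × interval) / 36.

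- As defined: (3 + 0 + 12 + 3 + 9 + 0 + 12 + 3 + 6 + 0)/36 = 48/36 = 1.33 months.
- To the next required scan: (9 + 0 + 27 + 18 + 9 + 0 + 45 + 36 + 36 + 0)/36 = 180/36 = 5.0 months.
- Ratio: 1.33/5.0 = 27%.
- Share confirmed on a triggered scan: (3 + 3 + 3 + 3 + 3 + 6)/36 = 21/36 = 58%.

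**Sensitivity to onset.** With onset uniform over 0 to 18 months only: 27/18 = 1.5 months as defined against 63/18 = 3.5, a ratio of 43%.

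**Sensitivity to local scans.** Suppose local scans were planned at 12 and 24 months (an assumption). Over 0 to 36 months, lead time as defined becomes (3 + 9 + 9 + 9 + 6)/36 = 1.0 month, from the 3, 9, 15, 21 and 30m rows. The interval to the next planned scan becomes (9 + 9 + 9 + 9 + 36)/36 = 2.0 months. The ratio is 50%, and the absolute gap falls from 3.7 months to 1.0.

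**Allowing a true lag between miRNA and imaging.** A simulation of 200,000 relapses per scenario used near-uniform onset, a triggered scan 0.5, 1.0 or 1.5 months after the sample, and repeat scans 3 and 9 months after a negative triggered scan. It assumed perfect tests and left out PET-CT, markers and local scans.

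| Imaging lag (months) | Mean as defined | Mean to next required scan | Ratio | Share dated by a triggered scan |
|---|---|---|---|---|
| 0 | 1.05–1.62 | 5.0 | 21–32% | 58% |
| 1 | 1.36–1.76 | 6.0 | 23–29% | 64–65% |
| 3 | 2.59–2.82 | 8.3 | 31–34% | 74–77% |
| 6 | 6.18–6.67 | 12.0 | 52–56% | 83–90% |

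The direction is the same throughout; the size depends on the lag.

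**After 36 months** no required scan follows the stored 42-month sample or the real-time 48- and 60-month samples, so this comparator does not exist there.

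**The case against.** The strongest reply is that the design partly anticipates the problem. Four samples are withheld from centres, and section 9.1.1 gives information on lead time as their purpose. Positives at 6, 18 and 36 months are confirmed on the routine scan. If a triggered scan is negative and relapse appears later, the interval contains a real lag. Central review (section 11.3.3) re-dates when relapse could be seen. All of this is correct, and it rules out a reading that a colleague might draw from the definition: that lead time records scheduling delay and nothing else. It does not restore the comparator. A stored sample moves only the miRNA date: a first positive at 21 months confirmed after the 24-month trigger gains 3 months, against 15 months to the 36-month scan. Central review can re-read only scans that were done.

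Second, standard surveillance is more than three scans. Section 1.1.2 describes 3 to 7 over five years, section 7.2.1 allows local scans, and markers are taken at every visit. This stands: the interval to the next required scan is an upper-end comparator.

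Third, a breakdown by type of scan may be in the separate analysis plan. It may, but the protocol itself fixes the endpoint definition, and a plan that follows it inherits the problem.

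Fourth, a reader might infer that the error feeds into the Part B design or the economic case. The protocol does not support that. Part B is randomised on advanced relapse, and its cost-effectiveness analysis uses its own questionnaires and routine data. Lead time is first analysed at the final Part A analysis (section 11.3.1), where the IDMC weighs secondary data by judgement; no numerical criterion uses it.

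**Conclusion.** The point holds for a defined group: relapses whose confirming scan was triggered by a real-time positive at 3, 12, 24 or 30 months, including those first positive on a stored 9- or 21-month sample. For these, lead time as defined understates how far diagnosis is brought forward and does not estimate the quantity in section 2.2. Positives at 6, 18 and 36 months, the stored 15-month sample, and triggered scans that are negative at first are unaffected or only partly affected.

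Under the stated assumptions the mean as defined is roughly 20 to 56% of the interval to the next required scan, an understatement of about 44 to 80%. Quoting 80% alone would take the extreme of an assumption-dependent range. Local scans or marker detection would narrow the gap. The bias runs against miRNA, the endpoint is secondary and descriptive, and the progression rule of at least 10 of 11 relapses is not affected. It is worth correcting before lead time is analysed, so that the definition is not changed after the data are seen.

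**What to change.** In sections 11.2.2 and 11.3.3:

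1. Classify each confirming scan as routine (required, or local and already planned) or miRNA-triggered.
2. Report the observed sample-to-scan interval by that class, and call it time to confirmation where the scan was triggered.
3. For the comparison with standard surveillance, add an estimate that treats triggered detection as censoring the imaging-only detection time. Alternatively, run the interval to the next scheduled scan (required, or local where planned) and label it an upper-end estimate. Censor relapses after the last scheduled scan.

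The cost is modest: a reason recorded for each confirming scan, and each participant's planned local scans recorded in advance, since dates of completed scans alone will not show what had been planned. If most relapses are dated by triggered scans, as in the simulation, an estimate based on censoring alone will be thin, which is a reason to show both versions. The estimate against the schedule assumes that imaging would have been on time and would have shown the relapse, so it should stand beside the observed interval. Clinical management, visits and sampling stay as they are.

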11.2.3. Part B Primary Endpoint

The primary endpoint for Part B is the number of advanced relapses, defined as those with mass size (maximum short axis diameter) $\geq 3\text{cm}$ and/or clinical stage III. The time point of interest is 3 years and Kaplan-Meier estimation will be used, with censoring at the last disease assessment for those participants lost to follow-up before 3 years.

11.2.4. Part B Secondary Endpoints

The following secondary endpoints will be evaluated during part B:

- Number and type of imaging investigations performed
- Patient-reported acceptability of the different surveillance approaches
- Patient-reported anxiety and fear of recurrence (from Fear of Recurrence short form, FCR4⁴¹)
- Patient-reported health-related quality of life (from EORTC survivorship module, SURV100⁴²)
- Disease-free survival (DFS), defined as time from randomisation to disease recurrence or death from any cause with observations censored at most recent follow-up assessment for participants who remain alive and disease-free
- Overall survival (OS), defined as time from randomisation to death from any cause with observations censored at date last known to be alive for surviving participants
- Treatment for relapse
- Incidence of second malignancies
- Cost-effectiveness based on patient-reported health status and health resource usage

11.3. Statistical Analysis Plan

All statistical analyses will be performed at the ICR-CTSU. Planned analyses for Part A are outlined here in brief. Details of the planned analyses in Part B, including timing and analysis sets, will be added via an amendment prior to commencement of Part B. Full details of analysis methods will be specified in Statistical Analysis Plans (SAPs) for Part A and Part B in accordance with ICR-CTSU Standard Operating Procedures.

The Part B health economics analysis will be carried out by the University of York. A summary of the planned analyses will be added to the protocol prior to commencement of Part B and will be detailed in full within a separate Health Economics Analysis Plan (HEAP).

